6.10. Efficacy Analyses

The analysis of the viral load lab results will utilize the following conventions:

For qualitative endpoints in the trial (viral clearance yes/no, time to viral clearance) the lab determination of "positive"/"negative" will be used. SARS-CoV-2 clearance (yes/no) is defined as 2 consecutive negative tests for the SARS-CoV-2 virus. The date of viral clearance is defined as the earliest date of the 2 consecutive negative tests.

For quantitative endpoints in the trial (change from baseline, area under the response viral load curve [AUC]), the viral load will be derived based on cycle threshold (Ct) values with the following considerations:

- Two Ct values will be provided on 2 different genes: N1 and N2. N1 will be used as the primary measure; N2 will only be used when the Ct value for N1 is not available.
- Ct values range between 0 and 45.
- Negative CoV-2 tests will be associated with a Ct value of 45.
- For any sample with a positive CoV-2 test result, an additional normalization step will be taken in the analysis. The viral load Ct value described in the previous steps

will be subtracted by (RP Ct -26.17), where RP Ct is a measure for the amount of material in the sample, and 26.17 is a historical average value of RP Ct for this assay, used here to center the RP Ct values. This step will be skipped if a valid RP Ct value is unavailable for the sample.

• The (log base 10) viral load will be calculated from the Ct value (45-Ct)/log₂10, or (45-Ct)/3.321928.

A lower Ct value of 40 for negative CoV-2 tests may be explored as part of exploratory PK/PD exposure-response analysis (Section 6.11).

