6.10.1. Primary Outcome and Methodology

The primary endpoint is the proportion of participants with SARS-CoV-2 viral load greater than 5.27 on Day 7, corresponding to Ct value of less than 27.5 based on nasopharyngeal swab sampling for RT-PCR testing for SARS-CoV-2. Statistical hypotheses testing for the primary endpoint will be conducted using a logistic regression model at the two-sided 0.05 level.

The proportion of participants with SARS-CoV-2 viral load greater than 5.27 on Day 7 will be statistically analyzed using a logistic regression with a Firth penalized likelihood (Firth 1993). The Firth correction can be implemented in PROC Logistic by including 'firth' as an option in the model statement. The odds ratio and the corresponding CIs, as well as the treatment differences and the corresponding CIs, will be reported. If the number of observed events is less than 5 in any treatment arm an exact test (i.e. Fisher's exact) will be conducted instead of using a logistic regression.

If Day 7 SARS-CoV-2 viral load is missing, then Day 7 will be imputed using RSI as described in Section 6.3.4 for Treatment Arms 1-6 and LOCF described in Section 6.3.5 for Treatment Arms 7-13.

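### Positive swabs are normalised with no floor on viral load, so a weak positive can be scored below a negative swab in the secondary viral-load analyses

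*SAP*

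**What the plan says.** SAP Section 6.10 lists the conventions for deriving viral load, in this order:

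- Range: "Ct values range between 0 and 45".
- Negatives: "Negative CoV-2 tests will be associated with a Ct value of 45".
- Positives only: "For any sample with a positive CoV-2 test result, an additional normalization step will be taken in the analysis". The Ct from the preceding steps "will be subtracted by (RP Ct -26.17), where RP Ct is a measure for the amount of material in the sample". The constant in that formula centres the correction on the assay's past mean RP Ct.
- Exception: "This step will be skipped if a valid RP Ct value is unavailable for the sample".
- Conversion: the log10 "viral load will be calculated from the Ct value (45-Ct)/log₂10, or (45-Ct)/3.321928".

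After the list comes an option: "A lower Ct value of 40 for negative CoV-2 tests may be explored as part of exploratory PK/PD exposure-response analysis".

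Nothing bounds the normalised Ct or the resulting load. Two other rules give the size or the zero value of the load a special role. Section 6.1.2 keeps the higher load when two records share the same sample date and time. Section 6.16.2.12 shifts every non-zero load by 0.158 per day since symptom onset and leaves loads of exactly zero alone.

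**The concern.** Negatives are fixed at a load of 0 and are not normalised, while positives are shifted in either direction by the amount of material in the swab. When the swab is rich in material (RP Ct below 26.17), the normalised Ct goes up and the load goes down. Close to Ct 45 it can go past the value reserved for negatives. A swab in which virus was detected then counts as having less virus than one in which none was detected.

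At stake are the secondary analyses that use the load as a number:

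- the change-from-baseline mixed model and the geometric mean ratios (Section 6.10.3.1.1);
- baseline viral load wherever it is a covariate;
- the duplicate rule in Section 6.1.2, which would keep a negative record (0) over a simultaneous weak positive (-0.30);
- the plots in Section 6.16.2.12, where a sub-zero load is neither the zero the rule protects nor an ordinary positive value.

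The range statement does not clearly settle the matter. It comes before the normalisation step, so one programmer may read it as describing the assay output and another as a ceiling on the final Ct. They would produce different data.

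**Working it through.** **Inputs from SAP Section 6.10.** Negatives at Ct 45; normalised Ct = Ct - (RP Ct - 26.17) for positives; load = (45 - Ct)/3.321928; optional Ct 40 for negatives. The spread of RP Ct and the Ct up to which a swab is called positive are not given and are assumed below.

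**The plan's own figure.** (45 - 27.5)/3.321928 = 5.268, which rounds to the stated 5.27. The conversion is reproduced.

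**When a positive falls below a negative at Ct 45.** This needs Ct - (RP Ct - 26.17) > 45, that is, RP Ct < 26.17 - (45 - Ct).

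| Raw Ct | RP Ct must be below | Example RP Ct | Normalised Ct | Load |
|---|---|---|---|---|
| 40 | 21.17 | 20 | 46.17 | -0.352 |
| 42 | 23.17 | 22 | 46.17 | -0.352 |
| 43 | 24.17 | 23.17 | 46.00 | -0.301 |
| 44 | 25.17 | 24 | 46.17 | -0.352 |

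A negative swab scores 0 throughout.

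**How often.** Assume RP Ct is normal about 26.17. At a fixed raw Ct the chance of inversion is Phi(-(45 - Ct)/SD):

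| | SD 1.5 | SD 2 | SD 3 |
|---|---|---|---|
| Ct 43 | 9.1% | 15.9% | 25.2% |
| Ct 44 | 25.2% | 30.9% | 36.9% |
| Positives uniform on Ct 38-45 | about 9% | 11.4% | 16.9% |
| Positives uniform on Ct 35-40 | about 0% | 0.1% | 1.2% |

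The last two rows show that the upper limit for calling a swab positive matters more than the spread of RP Ct.

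**How much.** For positives uniform on Ct 38-45, the mean amount by which the normalised Ct exceeds 45 (counting zero where it does not) is close to SD²/(4 × 7). SD 1.5 gives 2.25/28 = 0.080 Ct, or 0.080/3.321928 = 0.02 log10. SD 3 gives 9/28 = 0.321 Ct, or 0.10 log10. If the share of such swabs at a visit differed between arms by 20 percentage points (an assumption), the treatment difference would move by 0.2 × 0.02 to 0.2 × 0.10, about 0.005 to 0.02 log10.

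**Ct 40 option.** Negatives rise to (45 - 40)/3.321928 = 1.505. Inversion now needs only RP Ct < 26.17 - (40 - Ct): below 24.17 at Ct 38 and below 26.17 at Ct 40. A raw Ct above 40 inverts even at the average RP Ct: Ct 42 scores 0.903, which is 0.602 below a negative. For positives uniform on Ct 35-40, 8% to 23% invert for SD 1 to 3. A cap at 45 does not cure this, because positives with normalised Ct between 40 and 45 still score between 0 and 1.505.

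**Other outcomes.**

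- Primary endpoint: the inversion occurs where the normalised Ct exceeds 45, and the cut is at 27.5. Replacing a sub-zero load by 0 cannot carry it across 5.27. The same holds for values carried forward to Day 7.
- Clearance: it uses the laboratory's positive or negative call, so no normalised value enters.
- AUC (Section 6.10.3.1.3): it uses only values above a lower limit of quantification that the SAP does not define. Sub-zero loads enter only if they count as above it.
- Plots: a load of -0.301 is shifted upward and passes 0 only after 0.301/0.158 = 1.9 days of symptoms, so its order against negatives depends on symptom duration.

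**The case against.** The strongest reply is that this hardly matters. If positives are called only up to about Ct 40, inversion against Ct 45 is close to zero. Even with positives running to Ct 45, the mean shift is at most about 0.1 log10 among the weak positives and much less in a difference between arms. The exposed analyses are secondary and not controlled for multiplicity. The Ct 40 value is optional, belongs to exploratory exposure-response work, and the SAP does not say how positives above Ct 40 would be handled there. All of this stands, and it limits the weight of the point.

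It can also be said that the 0 to 45 range already acts as a ceiling. That is possible, but the range is listed before normalisation, which works on the Ct from the steps before it. For the same reason it cannot be claimed that the plan breaks its own range. The text simply does not say.

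A third reply is that flooring one side of a centred correction censors low values and ties detected with undetected swabs. That is true and is the price of the fix. But negatives already sit at 0 without any correction, so the scale has a floor for them and none for positives.

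A reader might go further and infer that the primary endpoint is stated in two non-equivalent ways, since Section 6.10.1 describes the load cut-off as "corresponding to Ct value of less than 27.5 based on nasopharyngeal swab sampling" without saying that the Ct is normalised. The SAP does not support this. The endpoint is defined on viral load, the only derivation of viral load includes normalisation, and the conversion that follows that step turns 27.5 into 5.27. A separate endpoint on the raw Ct is nowhere specified.

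**Conclusion.** The concern holds in a limited form. As written, the derivation can place a detected swab below an undetected one, and no later rule prevents it. The exposure is mainly in the change-from-baseline mixed model and geometric mean ratios, the baseline viral load covariate, the duplicate-record rule and the adjusted plots, and in AUC only under one reading of the undefined quantification limit. The primary endpoint and clearance are not affected.

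The ordering error follows from the SAP's formula alone. Its frequency does not: the range from about 0-1% to about 9-17% of weak positives rests on an assumed normal RP Ct with standard deviation 1.5 to 3 and on assumed ranges of Ct among positives. The effect on treatment estimates is likely to be small. That weak positives would be more common late, or in an arm that clears faster, is plausible but is not a figure in the document. The point is worth correcting because the correction is almost free, not because it threatens the trial's conclusions.

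**What to change.** Add to SAP Section 6.10, after the normalisation bullet, that a normalised Ct above 45 is set to 45, so that the load is never below 0. Add to the Ct 40 option that, when it is used, positives with a normalised Ct above 40 are also set to 40. With the floor in place, the duplicate rule in Section 6.1.2 can no longer prefer a negative with a higher load than a positive.

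The cost is SAP wording and one line in the viral-load derivation, with no new data. The drawback is that a few detected swabs are tied with negatives at the floor, and the plot rule in Section 6.16.2.12 would then leave them unshifted as it does negatives. The positive or negative call remains available for the clearance analyses, so the distinction is not lost.

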6.10.1. Primary Outcome and Methodology

The primary endpoint is the proportion of participants with SARS-CoV-2 viral load greater than 5.27 on Day 7, corresponding to Ct value of less than 27.5 based on nasopharyngeal swab sampling for RT-PCR testing for SARS-CoV-2. Statistical hypotheses testing for the primary endpoint will be conducted using a logistic regression model at the two-sided 0.05 level.

The proportion of participants with SARS-CoV-2 viral load greater than 5.27 on Day 7 will be statistically analyzed using a logistic regression with a Firth penalized likelihood (Firth 1993). The Firth correction can be implemented in PROC Logistic by including 'firth' as an option in the model statement. The odds ratio and the corresponding CIs, as well as the treatment differences and the corresponding CIs, will be reported. If the number of observed events is less than 5 in any treatment arm an exact test (i.e. Fisher's exact) will be conducted instead of using a logistic regression.

If Day 7 SARS-CoV-2 viral load is missing, then Day 7 will be imputed using RSI as described in Section 6.3.4 for Treatment Arms 1-6 and LOCF described in Section 6.3.5 for Treatment Arms 7-13.

6.10.2. Additional Analyses of the Primary Outcome

6.10.2.1. Bayesian Modeling

A Bayesian logistic regression model will be fitted to evaluate the success criteria by the Lilly statistics group with the model listed below:

$$\begin{aligned} r_{ij} \sim &Binomial(p_{ij}, 1) \\ &\log\left(\frac{p_{ij}}{1 - p_{ij}}\right) = \beta \times base_{ij} + \alpha_i \end{aligned}$$

Where,

 r_{ij} : is 0 if patient j on treatment i has a SARS-CoV-2 viral load greater than 5.27 on Day 7 and 1 otherwise

 $base_{ij}$: is the baseline viral load for patient j on treatment i

 β : a fixed coefficient on the covariate log base 10 baseline viral load

 α_i : a parameter corresponding to treatment i (with i=1 being the placebo group).

and priors:

$$\beta \sim N(0,100^2)$$

 $\alpha_1 \sim \pi(\alpha_1)$

At least 2 priors $(\pi(\alpha_1))$ will be considered for α_1 , a diffuse $N(0,100^2)$ and an informative prior based on available information at the time of analysis.

6.10.3. Secondary Efficacy Analyses

6.10.3.1. SARS-CoV-2 Viral Load

6.10.3.1.1. Change from Baseline in SARS-CoV-2 Viral Load

Changes from baseline to Day 3, Day 5, Day 7, and Day 11 in SARS-CoV-2 viral load data in the log base 10 scale will be statistically analyzed using a linear mixed-effect model. The model will contain log base 10 transformed baseline as a covariate, treatment, day, treatment-by-day interaction) as fixed effects. The LS means and treatment differences (active treatment minus placebo) will be calculated and presented with their corresponding 95% CIs. In addition, the geometric mean ratio to baseline and corresponding standard error for each treatment, the ratio of geometric mean ratio to baseline vs placebo, and corresponding 95% CIs will be presented. All available data will be used in the analysis.

SARS-CoV-2 viral load, including changes from baseline, will be summarized and plotted by treatment and listed. Baseline is defined as the Day 1 predose assessment.

No imputations of missing data will be conducted.

6.10.3.1.2. SARS-CoV-2 Viral Load Among Participants Enrolled with ≤8 Days of Symptoms Prior to Randomization

Similar methodology, as described in Section 6.10.1, will be utilized on the subset of participants enrolled with ≤ 8 days of symptoms prior to randomization.

6.10.3.1.3. SARS-CoV-2 Viral Load AUC

The AUC from Day 1 predose to Day 11 (AUC[0-D11]) will be calculated according to the linear trapezoidal rule using the measured SARS-CoV-2 viral load-time values above the lower limit of quantification. No imputations of missing data will be conducted. No AUC(0-D11) values will be calculated when Day 1 predose and/or Day 11 values are missing, or if there are more than 1 value missing in the profile.

The AUC will be summarized and plotted by treatment and listed.

Additionally, AUC data will be statistically analyzed using a linear model. The model will contain treatment as a fixed effect, log base 10 transformed baseline viral load as a covariate. The least square (LS) means and treatment differences (active treatment minus placebo at each dose level) will be calculated and presented with their corresponding 95% CIs. All available data will be used in the analysis.

If deemed appropriate, the data may be log-transformed prior to analysis, and the LS means and treatment differences will be back-transformed.

A similar Bayesian model listed in Section 6.10.2, by removing the day, interaction, and within subject error term, will be applied for log base 10 transformed AUC measure analysis.

6.10.3.1.4. 75th Percentile of SARS-CoV-2 Viral Load

For treatment groups 9-11, the 75th percentile of SARS-CoV-2 viral load on Day 7 will be statistically analyzed using a quantile regression analysis. The model will contain treatment as a fixed effect. The conditional 75th percentile and treatment differences (active treatment minus placebo) will be calculated and presented with their corresponding 95% CIs.

If Day 7 SARS-CoV-2 viral load is missing, then Day 7 will be imputed using LOCF described in Section 6.3.5.

For treatment groups 12-14, the 75th percentile of SARS-CoV-2 viral load on Day 7 will be summarized descriptively.

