6.1.4. Analysis Methods

Unless otherwise specified, variables will be analyzed in the original scale on which they are measured. SARS-CoV-2 viral load data will be evaluated in log base 10 scale. The parametric approach will be employed by default for statistical analysis except when nonparametric analysis, such as by a rank-based method, Mann-Whitney, or van Elteren tests, is deemed to be more appropriate.

All hypothesis tests will be 2-sided at an alpha level of 0.05. No adjustment for multiplicity will be performed for Treatment Arms 1-8. For Treatment Arms 9-11, a hierarchical multiple comparisons procedure, which will control type I error in the primary endpoint analysis, will be implemented, see Section 6.5.

Any change to the data analysis methods described in the protocol will require an amendment only if it changes a principal feature of the protocol. Additional exploratory analyses of the data may be conducted as deemed appropriate, including pharmacokinetic/pharmacodynamic (PK/PD) model-based exposure-response analyses.

Table PYAH.6.3. Tables and Figures Related to Demographics and Other Characteristics of Study Population

Method	Analysis
Descriptive Statistics	Number of participants, mean, standard deviation, median, minimum, and maximum for continuous measures, and frequency counts and percentages for categorical measures
Kaplan-Meier curves and summary statistics, Cox proportional hazards	Treatment comparisons of time-to-event based endpoints
Logistic regression analysis	Treatment comparisons of binary variables with treatment in the model
Nonparametric	Treatment comparison of ordinal, nominal, and non-

(e.g., Mann-Whitney or van Elteren tests)	normally distributed continuous variables
Mixed-effects model repeated measures (MMRM)	Treatment comparisons of continuous efficacy and
analysis	health outcome variables

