6.3.1. Modified Non-Responder Imputation

For analysis of viral clearance (yes/no), missing data will be imputed using a mNRI. Specifically, for patients that have missing postbaseline data for reverse transcription polymerase chain reaction (RT-PCR) testing for SARS-CoV-2 (based on nasopharyngeal swab sampling) then viral clearance status will be imputed as follows:

- If a participant has previously achieved viral clearance (i.e. the participant previously had 2 consecutive negative tests), then viral clearance will be imputed as "Yes".
- If a participant has not previously achieved viral clearance (i.e. the participant does not have 2 consecutive previous negative tests), then viral clearance will be imputed as "No".

After imputation, data from all participants will be included in the analyses. The application of mNRI to viral clearance helps ensure that the maximum number of randomized participants.

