6.16.2.12. Viral Load Plots

The 7th octile (87.5th percentile) for the observed viral load data will be plotted across Days 1, 3, 5, 7, and 11 for all Treatment Arms. Additionally, the 4th (median), 5th (62.5th percentile), and 6th (75th percentile) octiles will be plotted separately.

The 4th, 5th, 6th, and 7th octile for viral load data adjusted for days from symptom onset at baseline will be plotted across Days 1, 3, 5, 7, and 11 for all Treatment Arms. Viral load participant data will be adjusted by multiplying the participants number of days from symptom onset at baseline by 0.158 (estimated mean daily decrease in viral load) and then adding the result to all of the participants non-zero viral load measurements. Note, that if the observed viral load is zero, it will not be adjusted.

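### The viral-load AUC drops negative swabs through an LLOQ filter, although Section 6.10 sets them to log10 load 0 for this endpoint, and the SAP does not say whether they count as missing

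*SAP*

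**What the plan says.** Section 6.10 sets the conventions for viral load results. The part on quantitative measures opens "For quantitative endpoints in the trial (change from baseline, area under the response viral load curve [AUC", so the AUC is expressly covered. It then states "Ct values range between 0 and 45" and "Negative CoV-2 tests will be associated with a Ct value of 45", and converts Ct to log10 load as (45 - Ct)/3.321928. Section 6.1.4 confirms the scale: "SARS-CoV-2 viral load data will be evaluated in log base 10 scale".

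Section 6.10.3.1.3 defines the AUC by the linear trapezoidal rule "using the measured SARS-CoV-2 viral load-time values above the lower limit of quantification". It rules out imputation and adds "No AUC(0-D11) values will be calculated when Day 1 predose and/or Day 11 values are missing", or when more than one value in the profile is missing. The SAP mentions an LLOQ nowhere else. It gives no figure for it and no rule for a result at or below it.

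Elsewhere the SAP treats a negative as data. Section 6.3.1 imputes clearance only "for patients that have missing postbaseline data for reverse transcription polymerase chain reaction (RT-PCR) testing for SARS-CoV-2". Section 6.16.2.12 says of the plots: "Note, that if the observed viral load is zero, it will not be adjusted".

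**The concern.** The two sections give different instructions for the same swab and the same endpoint. Section 6.10 supplies a value of 0 for a negative. Section 6.10.3.1.3 does not let that value in. No laboratory figure is needed to see this: an LLOQ of 0 would already exclude a value of 0, because only values above the limit enter.

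Once negatives are left out, two readings of Section 6.10.3.1.3 remain.

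- **(a) Left out but not missing.** The trapezoid ends at the last quantifiable value, or draws a straight line across an interior negative.
- **(b) Left out and missing.** A participant who is negative on Day 11, or at two or more visits, has no AUC. A single interior negative is still bridged.

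Under (a) the AUC is wrong for participants with a negative swab. Under (b) participants leave the analysis because they cleared virus, and more of them leave the faster-clearing arm, which dilutes a real effect. In Arms 1-11 this AUC is compared with placebo, with 95% confidence intervals. As written, the choice between readings would fall to whoever programs the analysis.

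**Working it through.** **Scale.** From Section 6.10, Ct 27.5 gives (45 - 27.5)/3.321928 = 5.268, which matches the 5.27 in the primary endpoint. Ct 45 gives (45 - 45)/3.321928 = 0.

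**Exact effect on a profile.** Swab days are 1, 3, 5, 7 and 11 (Section 6.16.2.12). V5, V7 and V11 are the log10 loads on those days. The profiles are invented; the formulas are exact.

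- *Negative on Day 11 only.* The lost last segment is (V7 + 0)/2 x 4 = 2 x V7. For 6, 4, 3, 2, 0 the segments are 10 + 7 + 5 + 4 = 26 with the zero kept. Ending at Day 7 gives 22, short by 2 x 2 = 4. Under (b) there is no AUC.
- *Negative on Day 7 only.* Bridging Day 5 to Day 11 gives (V5 + V11)/2 x 6 = 3 x (V5 + V11). With the zero kept, the same stretch is V5 + 2 x V11. The excess is 2 x V5 + V11. For 6, 4, 2, 0, 1 the AUC is 10 + 6 + 2 + 2 = 20 with the zero kept and 10 + 6 + 9 = 25 bridged, an excess of 2 x 2 + 1 = 5.
- *Rank reversal.* The profile 6, 4, 2, 1, 1 gives 10 + 6 + 3 + 4 = 23. The profile 6, 4, 2, 0, 1 is never above it at any visit, yet scores 25 when bridged and 20 with the zero kept.

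**Illustrative simulation.** Only 122 per arm comes from the SAP (Section 5.2, Arms 9-11). Assumed: baseline mean 6 (SD 1.8); mean decline 0.40 v 0.50 log10/day; a value below 0, 0.5 or 1.5 is negative; slope SD/noise SD of 0.05/0.5, 0.15/0.8 or 0.10/1.4. That makes nine scenarios of 1500 trials each. Each value is baseline - slope x (day - 1) + noise. The AUC is regressed on treatment and baseline load, tested two-sided at 0.05.

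| Handling of negatives | Difference, active minus placebo (log10-days) | Power |
|---|---|---|
| Kept as 0 | -4.2 to -4.7 | 78-100% |
| Reading (a) | -4.7 to -5.8 (9-22% larger) | 84-100% |
| Reading (b) | -2.3 to -4.3 | 22-100% |

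Two scenarios show the spread for reading (b) against zeros kept:

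- Cut-off 0, slope SD 0.05, noise SD 0.5: -4.3 against -4.5, power 100% both ways. An AUC remains for 85% of the slower and 70% of the faster-declining arm.
- Cut-off 1.5, slope SD 0.15, noise SD 0.8: -2.5 against -4.5, power about 37% against 93%. An AUC remains for 58% and 42%.

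With no true effect (0.40 v 0.40, cut-offs 0 and 1.5) every handling gave a difference near 0 and type I error of 4-6%.

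**Second set of assumptions.** This used baseline 6.5 (SD 1.8), decline 0.6 on placebo v 0.75 or 0.9 on active (SD 0.15), error SD 1 and LLOQ 0. The unadjusted difference was -5.5 or -10.1 with zeros kept, -6.2 or -11.2 with zeros dropped, and -0.8 or +0.1 with zeros counted as missing. In the last case 65% or 84% of active and about 42% of placebo participants had no AUC.

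**The case against.** The strongest reply is that Section 6.10 simply governs: it names the AUC and sets negatives to 0, so zeros enter and the LLOQ phrase is a leftover without numerical effect. That is the sensible result, and it is the reference case above. But reaching it means setting aside an explicit restriction in the section that defines the endpoint.

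It can also be said that the SAP's own text weakens both readings. Sections 6.3.1 and 6.16.2.12 keep negatives apart from missing data, which speaks against (b). A curve ending on Day 7 is not an AUC to Day 11, which speaks against (a). Both remarks are fair, but together they leave no computable AUC for a participant negative on Day 11, so the rule needs correcting.

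On size, much of the objection stands. The rank reversal needs an isolated interior negative followed by a quantifiable Day 11 value; in a re-run of the nine scenarios, participants with a single bridged interior negative were 0.0% to 3.7% of the total. Reading (a) costs no power in these scenarios. The loss under (b) runs from none to severe, entirely on assumed inputs.

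Last, positives are normalised and negatives are not. With assumed Ct 44 and RP Ct 24, a positive becomes Ct 44 - (24 - 26.17) = 46.17, or log10 load (45 - 46.17)/3.321928 = -0.35, below a negative. This is true, but it comes from Section 6.10 and already affects the change-from-baseline model. It is not a reason to exclude negatives from the AUC.

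**Conclusion.** The concern holds and should be fixed. The conflict in wording and the profile arithmetic are certain. For a participant with a negative swab, neither reading of Section 6.10.3.1.3 gives the AUC that Section 6.10 implies.

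The effect on the treatment comparison cannot be fixed from the SAP. The simulated figures rest on assumed decline, variability and cut-off, and are not bounds. What does not depend on them is that reading (b) selects participants on outcome.

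Reach is limited. The AUC is a secondary endpoint without multiplicity control in a study the SAP calls nonconfirmatory. It is descriptive only in Arms 12-14 and in the addendum substudies that reuse the rule. The primary Day 7 endpoint and the change-from-baseline model are unaffected, and no inflation of type I error appeared in the scenarios tried.

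**What to change.** In Section 6.10.3.1.3, replace the restriction to values above the LLOQ with a statement that all measured values enter the AUC, with negative tests set to log10 viral load 0 (Ct 45) as in Section 6.10. Add that, for the Day 1, Day 11 and more-than-one-missing rules, only a swab not taken or not evaluable counts as missing.

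The cost is one or two SAP sentences and a programming check. No new data are needed.
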